10. SELECTION AND WITHDRAWAL OF SUBJECTS

During the prenatal visit (PNV = T0; some weeks before the due date) the pregnant women receive information about the the study and the use of VRH from the midwife. Each patient will be asked for participation in the study, after verifying the presence of the inclusion criteria and absence of any exclusion criteria. The registration checklist is filled in (questionnaire 1). If patients refuse, their motivation will be noted on the refusal questionnaire(questionnaire 4). All the included patients receive sufficient information and time to decide if they want to participate or not. After signing the informed consent (Questionnaire 2 resp) they will be immediately randomized using block randomization (with excel). This will assign the pregnant woman to either control group or the VRH group.

On the day of delivery every included patient will receive standard of care. When the women selected in the VR group are in active labor (NRS pain ≥ 4 , cervical dilatation ≥ 4 cm and regular contractions (every five minutes) we present the VRH treatment (T1).

Patients who refuse the VRH treatment (T1) or remove the VRH headset during(T2) will be asked to fill in questionnaire 4 (refusal questionnaire). They will be considered as drop outs.

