5. STUDY OBJECTIVES

5.1 PRIMARY OUTCOME

The primary endpoint is to compare the differences in NRS pain measured before and after the intervention during labor. (T3 minus T1) The Pain Numerical rating Scale (NRS) is a scale from 0 to 10 well known by the medical staff.^{xv xvi}

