9. SCHEDULE OF ASSESSMENTS AND PROCEDURES

RCT T	TO	T1	T2	T3	T4	T5	T6
Delivery Phase	Prenat consult	Active Labor (study threshold) Day 0	Labor	Labor	Labor	End of Delivery	Day 1
		Before the Start AQUA	During AQUA	End AQUA	T3+30 min		
Screening/ ICF	X						
Refusal questionnaire	X						
Patient Questionnaires & Observation							
NRS pain		X		X	X		
Nausea		X		X	X		
Likert satisfaction							X
CPOT (VR comfort scale)			X				
Willingness to repeat (intervention)							X
Recommend (intervention)							X
Practitioner questionnaire							
Monitored contractions (on the CTG during intervention)				X			
Satisfaction midwife						X	
Quality of the therapeutic relationship						X	
Objective criteria							
Vital signs (Saturation)		X	X	X	X		
Medication received							X
Epidural				X	X		
Progression of labor							X
(Serious) adverse events		X	X	X	X	X	
Stop of digital sedation session				X			

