11.3 CONCEALMENT MECHANISM AND IMPLEMENTATION

On the prenatal visit an investigator randomizes included patients (after they signed the IC) and gives them a study number as described in section '13.4 confidentiality and access to data'. A pop up in their electronic file and all the 4 questionnaires are kept together in one plastic sheet (one folder with 4 questionnaires per patient: registration checklist, informed consent, data collection form and refusal questionnaire) in a closet of the prenatal visit. Every day all folders of included patients are moved from the prenatal visit to the maternity ward (by the study nurse) where there is also a predetermined closed closet to store all the forms.

When the patient arrives on the labor ward to give birth (due day) the midwives are aware of their participation in the study thanks to the pop up in their electronic file. On this day, we explain again the study to the patient and give them the possibility to drop out. The reason why is always noted on Questionnaire 4 (refusal questionnaire).

The investigators (AB, LP, IS , FP) will not be blinded to the allocation because they can see if patients have the VRH experience or not during measurements.

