14. DATA HANDLING AND RECORD KEEPING

14.1 DATA COLLECTION METHODS AND RETENTION

There are four paper forms per patient that are used to collect the data that we put together in one plastic sheet (folder). Questionnaire 1 is the registration checklist where inclusion and exclusion criteria are checked, the study number and randomization group is noted. Questionnaire 2 is the informed consent signed by the patient and the investigator. Questionnaire 3 is the data collection form used by the investigators to note all the outcomes previously described. Questionnaire 4 is a refusal questionnaire where all reasons of refusal or interruption of the VRH can be assessed standardized.

The investigators earned the Oncomfort Academy certificate and a Good Clinical Practice certificate. Midwives on the ward have already a year of experience with the VRH therapy for labor pain.

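### The T1 pain score is a condition for offering the headset and the baseline of the primary outcome, yet nothing hides the allocation until it is recorded

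*Combined protocol and SAP*

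**What the plan says.** **Allocation.** Section 10 places randomisation at the prenatal visit, some weeks before the due date: "After signing the informed consent (Questionnaire 2 resp) they will be immediately randomized using block randomization (with excel". Section 11.3 has an investigator do this. Section 14.1 says that on Questionnaire 1 "the study number and randomization group is noted", and section 11.3 has the folder holding that form moved to the maternity ward before labour.

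**The gate.** Section 10 continues: "When the women selected in the VR group are in active labor", defined as NRS pain of at least 4, dilatation of at least 4 cm and contractions every five minutes, "we present the VRH treatment (T1". The synopsis also states these conditions for the intervention group. The schedule in section 9 heads the T1 column "Active Labor (study threshold) Day 0" and names no arm.

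**The baseline.** Section 5.1 defines the primary endpoint as to "compare the differences in NRS pain measured before and after the intervention during labor. (T3 minus T1". Section 9 schedules NRS pain at T1, T3 and T4 only, so there is no pain score before randomisation.

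**Blinding.** Section 11.3 says the investigators "will not be blinded to the allocation because they can see if patients have the VRH experience or not during measurements". It describes no step that keeps the group from the woman or the staff until T1 has been scored.

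**The concern.** One number does two jobs. The T1 NRS helps decide whether the headset is offered, and it is the value subtracted in the primary outcome. It is self-rated, it comes after randomisation, and the group is on paper in the ward folder by then. If knowing the arm changes how T1 is rated or recorded in one group, T3 minus T1 differs between arms without any analgesic effect.

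The gate supplies one concrete reason for this. A VRH woman who would score below 4, or the staff member at her bedside, can bring the offer forward with a score of 4.

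The stated reason for not blinding, that the headset is visible during measurements, cannot apply to T1, because section 9 places T1 before AQUA starts. T1 is the one component of the primary outcome that could be recorded without knowledge of the arm. The problem is separate from missing outcomes and from unblinded rating at T3.

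**Working it through.** **1. The plan's own figure.** Section 11.1 gives a difference of 2, SD 2, 80% power and two-sided 5%. A two-sample t-test (noncentral t) has 78.1% power at 16 per arm and 80.7% at 17, so 17 reproduces. With 10% drop-out, 17/0.9 = 18.9, giving 19 per arm and 38 in total. The sample-size arithmetic is not in question.

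**2. How a T1 shift enters the outcome.** Let VRH women rate T1 higher by b on average, with no true effect and T3 unchanged. The between-arm difference in change is E[T3 − (T1 + b)] − E[T3 − T1] = −b. All of b appears as benefit. If b is negative it hides benefit: a shift of −0.40 would reduce a true 2-point difference to 2 − 0.40 = 1.60.

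**3. How large b could be from the gate alone.** The documents give no distribution of T1. Assume the ungated NRS is roughly normal with SD 2 and mean 5 to 6. Take the extreme case in which every VRH woman below 4 rates up to exactly 4. With a = (4 − mean)/2, b = 2 × [φ(a) + a·Φ(a)].

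- Mean 5: a = −0.5, Φ = 0.309 (31% below 4), b = 2 × (0.352 − 0.154) = 0.40.
- Mean 6: a = −1.0, Φ = 0.159 (16% below 4), b = 2 × (0.242 − 0.159) = 0.17.

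Against the 2-point target these are 0.40/2 = 20% and 0.17/2 = 8%.

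**4. Effect on the false-positive rate.** The test is a two-sample t-test on T3 minus T1, 17 per arm, 32 df, critical value 2.037, noncentrality b/(SD_change × √(2/17)). Section 11.1 gives SD 2 for the NRS, not for the change. SD_change = 2√(2(1 − ρ)), where ρ is the T1–T3 correlation (assumed), so SD_change is 2 only when ρ = 0.5. At ρ = 0.5 the noncentralities are 0.167/0.686 = 0.24 and 0.396/0.686 = 0.58.

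| ρ (assumed) | SD_change | b = 0.17 | b = 0.40 |
|---|---|---|---|
| 0.3 | 2.37 | 5.5% | 7.6% |
| 0.5 | 2.00 | 5.6% | 8.7% |
| 0.7 | 1.55 | 6.1% | 11.2% |

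The SD is held fixed although rating up to 4 would slightly narrow T1, so these rates are approximate. Section 11.4 names a paired t-test or Mann-Whitney test for the primary outcome. The two-sample test is used here because the stated aim and the sample size are between-arm.

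**5. Would analysis alone cure it?** Adjusting for T1 leaves a bias of ρ × b: at ρ = 0.5, 0.5 × 0.17 = 0.08 to 0.5 × 0.40 = 0.20 points. That reduces the problem without removing it. A between-arm comparison of T3 alone does not use T1, so a T1 rating shift cannot bias it.

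**The case against.** The strongest reply is that the plan makes this bias possible but does not show that it occurs, and that the incentive is narrow. Much of that stands.

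- **The gate is binary.** Once a woman scores 4 it gives no reason to score higher. Dilatation and contraction frequency must also be met, so raising the NRS alone does not open it. A reader might infer a shift of a full point, which at SD_change 2 would mean 29% false positives, or suppose that half of VRH women rate a point higher. Neither follows: under the assumptions above only 16% to 31% would be below 4, and the gate-driven shift stops near 0.40.
- **Controls may face the same threshold.** A reader might infer that controls have no reason to reach 4. The section 9 heading names no arm, and section 6 uses T1 to T3 for both groups. If the threshold also governs T1 in controls, part of the incentive is common to both arms and cancels.
- **Who knows the arm is partly inferred.** No section says the woman is told her group before T1. Section 11.3 says the electronic pop-up tells midwives of participation, and it should not be read as showing the group. What the documents do show is the group on a form in the ward folder, unblinded investigators, and no step preventing disclosure.
- **The direction is not fixed.** Women expecting the headset might score lower, or controls without it higher. Either would hide an effect.

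These points limit the size. They do not answer the absence of any protection for T1, or the fact that the reason given for not blinding cannot apply there.

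**Conclusion.** The point holds as an avoidable weakness of modest expected size. The baseline of the primary outcome is a self-rated, post-randomisation score, recorded when the arm can be known, and it is also one of three conditions for the offer of VRH. Any arm-specific rating passes in full into T3 minus T1.

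For the gate mechanism at its extreme, the shift is about 0.17 to 0.40 points and the false-positive rate about 6% to 9%. This rests on an assumed ungated mean of 5 to 6 with SD 2, a T1–T3 correlation of 0.5, 17 per arm and no true effect. With correlations of 0.3 to 0.7 the range is 5.5% to 11.2%. None of these assumptions except the 17 and the SD of the NRS comes from the documents.

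The documents do not support saying that T1 will be inflated, that the bias must favour VRH, or that the plan applies the threshold to one arm only. On the last point sections 9 and 10 differ in wording and must be reconciled. The change is worth making because it is cheap and the trial has only 38 women.

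**What to change.** 1. In sections 10 and 11.3, state that the T1 NRS, dilatation and contraction frequency are written on Questionnaire 3 with the time, by the same rule in both arms, before the allocation is opened.
2. At the prenatal visit assign only the study number. Put the group from the existing Excel list in a sealed, opaque, numbered envelope in the folder, prepared so that neither the enrolling nor the measuring investigators have seen it. An envelope does not mask an investigator who drew the allocation. Note the opening time.
3. Remove the group from Questionnaire 1 (section 14.1) and confirm that the electronic pop-up shows participation only.
4. Reconcile sections 9 and 10 on whether the threshold defines T1 for controls. Which clinical rule applies is for the investigators to decide.
5. In section 11.4, add a between-arm comparison of T3 as a pre-specified sensitivity analysis. It is unaffected by T1 rating and matches the sample-size basis in section 11.1, a difference in NRS means at final analysis.

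The cost is one envelope per folder, someone outside enrolment and measurement to prepare them, edits to a few sections and one form change. The sample size and treatment do not change. The downside is that the woman and staff learn the arm only at T1, leaving less time to prepare the headset. Bias in the unblinded T3 score remains.

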3. SYNOPSIS

STUDY TITLE	A randomized controlled, single centre, study evaluating the impact of Virtual Reality Hypnosis during labor										
SHORT TITLE	VRH4L (Hypnotic Virtual Reality for Labor pain relief)										
PROTOCOL NUMBER	2										
SPONSOR	Department of Anesthesia, Clinique Saint-Jean Bruxelles (SJ)										
STUDY POPULATION	Women during labor										
PHASE	Prospective interventional Randomized Controlled Trial (RCT)										
STUDY DESIGN	
This prospective interventional RCT will evaluate efficacy of Virtual Reality Hypnosis (VRH) in reducing pain during labor. Hypnosis is delivered as a standardized therapeutic intervention through virtual reality, using a digital sedation software. This VRH module is called AQUA[©] (Oncomfort SA) and is specifically designed for the management of pain and anxiety during labor.
 
Women who are planning to give birth at the St-Jean Hospital are recruited at prenatal consultation some weeks before the calculated delivery date. Only patients with a planned induced labor can be included. Patients who agree to participate sign an informed consent form.
 
38 patients will be randomized in two arms (19 patients in each cohort):
 
 Patients in the intervention groups will receive a session of the AQUA[©] Digital Sedation module when in active labor (cervical dilatation ≥ 4 cm, contractions every 5 minutes, NRS pain score $\geq 4/10$) on top of the standard of care Patients in the control group will receive standard of care only. 
Patients are allowed to discontinue the VRH session at any time. A study staff member is present during the session to explain the intervention and fill in the questionnaires. Furthermore, she/he ensures the patient is receiving appropriate clinical care throughout the duration of the intervention.
 
Information from patient's report will be collected before the intervention, after the intervention and up to the patient's discharge from the maternity on day after childbirth. A log will be kept of patients who refuse to participate in the study.
										

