To compare patient experience in both arms	
Measure of NRS pain after 30 minutes
 
Measure of satisfaction by Likert Scale (0 to 5)
 
Measure of nausea by Nausea and Vomiting Score (0 to 3)
 
Evaluation of comfort during intervention with the CPOT scale (Critical care Patient Observation Tool 0 to 8) and heart rate
 
Willingness to undergo a potential next labor with VRH
 
Willingness to recommend VRH to acquaintances
										
To assess selected safety and efficacy outcomes in both arms	
Progression of labor
 
Need for epidural
										

	
Need for medication: type and dosages during stay
 
Frequency and type of (severe) adverse events (SAEs) (mother and baby)
 
If the patient removes the headset during the session, motivation is documented.

	
To assess gynecologist and nurse satisfaction
 
Measure of satisfaction of the midwife and obstetrician by the Likert scale (0 to 5)
 
Quality of the therapeutic relationship between the midwife and patient (reported by the midwife in a NRS from 0 to 10)

	
Evaluation of vital signs
 
Oxygen saturation
 
Systolic and diastolic blood pressure
 
Heart rate (during and in between contractions)

NUMBERS OF PARTICIPANTS	38
INCLUSION CRITERIA	
 1. Age: ≥ 18 and ≤ 45 years 2. Pregnant with term gestation 3. Willing to adhere to the rules linked to the use of the VRH headset: turning off mobile phone, visit bathroom in advance, no new visitors and no interference of the partner other than when the woman would ask him so 4. Provision of written informed consent 5. Induced labor
EXCLUSION CRITERIA	
 1. Complicated pregnancy (HELLP,...) 2. Scheduled caesarian delivery 3. Receipt of epidural analgesia or opioid painkillers before start active labor phase 4. Low auditory acuity that precludes use of the device 5. Low visual acuity that precludes use of the device 6. Head or face wounds precluding use of the device 7. Schizophrenia 8. Epilepsy 9. Dizziness 10. Non-proficiency in French and/or Dutch (research language)

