4.1.1. Standard of care

The standard treatment (ST) for labor pain as used in our hospital contains massage, aquatherapy and postural exercises. This is always available for any woman in labor. The VR group receives digital sedation and when asked the ST. In comparison to the control group who receives only the ST when asked.

If ST is not sufficient, a patient can receive a pharmacological treatment or an epidural analgesia. However, in this study we will examine the efficacy of VRH before the use of epidural analgesia or pharmacological treatment.

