5.2 SECONDARY OUTCOMES

30 min after the end of the intervention the NRS pain is assessed once more. (T4)

During the intervention the comfort of the patient is evaluated. (T2) To do this we use the CPOT (Critical care Pain Observation Tool). CPOT is a comfort scale for (non)-ventilated patients in the intensive care unit. We decided to use this score, because during the VR experience we cannot communicate with the patient, which is similar as in sedated patients. And in our own experience we see that the parameters that we look at to evaluate the comfort of the patient during a VR sedation are very similar to this scale. (Facial expression, body movements, muscle tension and vocalization together make a score of 0 to 8)^{xvii} Vital signs like heart rate and blood pressure are parameters that are easily measured during the intervention and considered as objective for evaluating pain during labor. (T1,2,3,4) ^{xviii}

Nausea is also actively evaluated. Therefore we use the PONV rating scale from 0 to 3. (T1, T3, T4) Anxiety is evaluated with the NRS at the same time. (T1, T2, T3) We use the Likert satisfaction scale (from 0 to 5) to explore the satisfaction directly after their experience and the day after delivery. (T3, T6)

Willingness to repeat the intervention and to recommend the intervention can correlate with satisfaction of the overall experience. (T6)

Progression of labor is followed with the degree of the cervix dilatation, therefore we will not perform more cervical examinations than needed but interpret the measurement of the midwives/obstetricians. (T5)

The midwives are asked to evaluate the therapeutic link between themselves and the patient (NRS) after the women return to the maternity ward. (T5)

All the medication received during the stay on the delivery ward, adverse events and interruptions from the intervention is noted. (T3, T5)

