6. STUDY DESIGN

The VRH4L trial is an interventional, randomized, controlled, single-center, parallel group trial. Randomization will be done as a block randomization with a 1:1 allocation^{xix}

Clinique Saint-Jean Brussels (SJ), where the study takes place, is an academic hospital in the center of Brussels with around 2000 deliveries per year.

We create two groups: the VRH group and the control group. During the intervention (T1-3) the VRH-group receives a digital sedation in contrary to the control group who will not use the VRH headset.

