7.2. EXCLUSION CRITERIA

Patients meeting any ONE of the following criteria are not eligible for this study:

1. Complicated pregnancy (HELLP,...)
2. Scheduled caesarian delivery
3. Receipt of epidural analgesia or opioid painkillers before start active labor phase
4. Low auditory acuity that precludes use of the device
5. Low visual acuity that precludes use of the device
6. Head or face wounds precluding use of the device
7. Schizophrenia
8. Epilepsy
9. Dizziness
10. Non-proficiency in French and/or Dutch (research language)

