8. CONCOMITTANT MEDICATION AND TREATMENT

The standard labor pain management contains massage, aqua therapy and postural exercises. In our institution, opioid patient controlled intravenous infusion (Remifentanil) or N2O inhalation as analgesia in the first stages of active labor is not standard of care. Every women can ask for and receive (if no contra-indications) an epidural. In this study, however, we will only include patients without an epidural. After childbirth we use paracetamol and anti-inflammatory drugs as first line painkillers. When necessary opioids can be added.

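### Section 10 classes randomised VRH women who refuse or remove the headset as drop outs, the term section 11.1 uses for non-evaluable patients, while section 11.4 analyses everyone randomised; collection of their T3 pain scores is not secured

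*Combined protocol and SAP*

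**What the plan says.** Section 10 randomises women at the prenatal visit, directly after consent. VRH is offered later, at T1, in active labour. Those who then refuse it, or who "remove the VRH headset during(T2) will be asked to fill in questionnaire 4 (refusal questionnaire). They will be considered as drop outs".

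Other parts of the document bear on what that label means:

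- **Synopsis:** stopping is expected and permitted: "Patients are allowed to discontinue the VRH session at any time". Removal is listed among the safety and efficacy endpoints: "If the patient removes the headset during the session, motivation is documented".
- **Section 5.2:** "adverse events and interruptions from the intervention is noted".
- **Section 6:** the VRH arm receives the session "in contrary to the control group who will not use the VRH headset".
- **Section 9:** NRS pain is scheduled at T1, T3 and T4. T3 is defined by the end of the AQUA session, and a stopped session is logged in that same column.
- **Section 11.1:** 17 evaluable patients per arm become 19 randomised through a 10% drop-out allowance in each arm.
- **Section 11.3:** on the labour ward every participant may drop out; no arm is named.
- **Section 11.4:** ITT, meaning all randomised patients as allocated, is the default for efficacy and safety, subject to exceptions. A per-protocol (PP) set is also applied to the primary outcome. Its list of major violations is open-ended and does not name headset non-use.
- **Section 14.1:** Questionnaire 4 records reasons for refusing or interrupting VRH.

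**The concern.** The primary endpoint is the change in NRS pain, T3 minus T1. Section 10 gives a disposition to women already randomised, on the basis of something that can happen in one arm only. Sections 11.1 and 11.3 use the same word for patients who are not evaluable or who leave the study. Staff who follow that vocabulary could stop collecting scores when the headset comes off, or the analyst could leave these women out.

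The ITT definition does not repair this by itself, because it cannot supply a T3 score that nobody recorded. A pain score missed during labour cannot be recovered. If the women who remove the headset are those in whom pain is rising most, the VRH women left in the comparison look better than the arm as randomised.

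**Working it through.** **1. The plan's own figure (section 11.1).** Difference 2, SD 2, two-sided 5%, power 80%. The standardised effect is 2/2 = 1. The two-sample t-test calculation gives 16.71, so 17 per arm (power at 17 is 80.7%). Then 17/0.9 = 18.9, so 19 per arm and 38 in total. The stated numbers reproduce. Two of 19 is 10.5%, close to the planned rate.

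**2. The two readings side by side.**

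| Points to exclusion or end of follow-up | Points to a label only |
|---|---|
| Section 10: drop outs, under a heading on withdrawal | Section 11.4: all randomised, as allocated |
| Section 11.1: drop out separates 19 randomised from 17 evaluable | Section 9: the stop is logged at T3, where NRS pain is also due |
| Section 11.3: drop out means leaving the study | Section 14.1: Questionnaire 4 concerns refusal or interruption of VRH |

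Nothing in the available text decides between the columns. No session length is given, so T3 has no clock time for women who refuse or stop early, or for controls.

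**3. Size if scores are lost (illustration).** Assumptions: no true effect; 19 per arm; SD 2 for the change (section 11.1 states it for the pain NRS); the women lost are those worst on a score with correlation ρ to pain change; between-arm t-test, as section 11.1 implies (section 11.4 names a paired t-test or Mann-Whitney test). The documents give neither a stopping rate nor ρ.

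Bias with k of 19 VRH women lost = −ρ × SD × (sum of the k largest expected normal order statistics of 19) / (19 − k).

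The two largest are 1.844 and 1.380, sum 3.224. For k = 2: 2 × 3.224/17 = 0.379, so the bias is −0.379ρ. If one control is also lost, 2 × 1.844/18 = 0.205 comes back, leaving −0.174ρ.

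Simulation (100,000 trials per row) agrees with the formula:

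| ρ | VRH lost, control lost | Bias, points | VRH-favouring error | Two-sided error |
|---|---|---|---|---|
| 0.25 | 2, 0 | −0.09 | 3.5% | 5.3% |
| 0.25 | 2, 1 | −0.04 | 2.9% | 5.1% |
| 0.25 | 2, 2 | 0 | 2.6% | 5.2% |
| 0.5 | 2, 0 | −0.19 | 4.8% | 6.1% |
| 0.5 | 2, 1 | −0.09 | 3.8% | 5.7% |
| 0.5 | 2, 2 | 0 | 2.8% | 5.7% |
| 1.0 (worst case) | 2, 0 | −0.38 | 9.5% | 10.3% |

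At ρ = 0 the bias is nil. The nominal VRH-favouring error is 2.5%. Two-sided error rises a little even with equal losses, because trimming shrinks the variance. The one-arm effect is therefore the gap in VRH-favouring error: 3.5% against 2.6%, and 4.8% against 2.8%.

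**4. Power if everyone is kept.** Effect 2 in users and none in non-users (an assumption), SD 2, all 19 per arm measured. With 2 non-users the mean difference is 2 × 17/19 = 1.79 and power is about 75%. With 4 it is 2 × 15/19 = 1.58 and about 63%. With no non-users, power is 85%.

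**The case against.** The strongest reply is that section 11.4 already answers the analysis question. These women are randomised, ITT includes all randomised patients as allocated, and section 10 names no analysis set, so it does not create an exception. Using PP to validate the result reads naturally as supportive. The schedule and the description of Questionnaire 4 also fit a reading in which only the session ends. And the general exit in section 11.3 means that losses need not fall in the VRH arm alone.

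Most of this stands. A reader might infer that the plan excludes these women from the primary analysis, or that it is silent on the matter. The documents support neither: the ITT default keeps them in, and the defect is a conflict between sections 10 and 11.1 on one side and section 11.4 on the other. What the reply does not meet is data collection. Inclusion in ITT presupposes a T3 score, and the available text neither requires one after refusal or removal nor says when it would fall.

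Two further limits apply. The size rests on an assumed stopping rate and an assumed link to pain. The consent form and the data collection form are not among the pages available, and either might carry a follow-up rule.

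**Conclusion.** The point holds as an unreconciled conflict that could cost primary data in one arm, not as a planned exclusion. Severity is moderate and confidence medium.

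At about the planned loss rate the bias is modest: 0.09 to 0.19 points towards VRH for correlations of 0.25 to 0.5, with VRH-favouring error of 3.5% to 4.8%. It is about half that if one control is also lost. It is nil if removal is unrelated to pain, if losses are alike in both arms, or if the term is only a label. A reader might take the worst-case row (−0.38 points, 9.5%) as the expected harm; that requires removal to be perfectly correlated with pain, which nothing in the documents suggests.

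The point is still worth settling before enrolment, because the remedy is wording and the scores cannot be collected afterwards.

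**What to change.** 1. **Section 10.** Replace the drop-out sentence with: *They are recorded as discontinuing the intervention, remain in the study and are analysed in the VRH group; NRS pain is still collected at T3 and T4 unless the woman withdraws from data collection.*
2. **Section 9.** For women who do not complete a session, and for controls, set T3 at one fixed interval after T1 equal to the AQUA session length, which the sponsor must state.
3. **Section 11.4.** State that ITT is the primary analysis of the primary outcome and PP is supportive. In the PP list, replace the item on medication not administered, which does not fit a headset trial, with: *VRH session not started or not completed (VRH arm)*. That item removes women from one arm only, which is why PP cannot be primary.
4. **Section 11.1.** Say that the 10% covers patients without outcome data, not headset non-use.

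If some T3 scores are still missing, a simple sensitivity analysis giving VRH women who stopped worse-than-control values is enough. Imputation from arm and T1 alone should not be relied on: if T1 says little about the change, it mostly returns the mean of the women who stayed.

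**Cost.** Wording in four sections; the T3 and T4 readings are already scheduled. The price is dilution: if non-users gain nothing, ITT power is about 75% with 2 non-users of 19 and about 63% with 4, against the planned 80%. Section 11.1 should state this. How epidural or other analgesia before T3 is handled, and how women who never reach T1 enter ITT, are separate questions that these edits do not settle.
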